16.66 Patient's Perception of Cosmesis

All eligible patients who have undergone surgery that was not converted to a mastectomy will be included in these analyses.

Patient's perception of cosmesis will be assessed at their initial post-operative visit as well as 1, 6, 12, and 24 months following completion of WBI using the BREAST-Q® subscales: satisfaction with breasts, satisfaction with overall outcome, and physical well-being.

Patients registered after surgery will not partake in the pre-operative assessment but will be asked to complete subsequent cosmesis surveys.

The following statistical analyses will be conducted separately for those women who undergo an ALND and those who do not undergo an ALND.

16.661 At Each Time Point

The total score for each of these subscales will be determined using the BREAST-Q® scoring module

For each of the subscales, a 95 % binomial confidence interval for the proportion of patients reporting deficits in that domain will be constructed. Also, a 95 % binomial confidence interval for the proportion of patients indicating that their cosmesis result on the one item questionnaire was poor or fair (scores: 3 or 4) will be constructed. For each of the three subscales, a Wilcoxon rank sum test will be used

to assess domain score differs between those women reporting a poor/fair cosmesis result on the one item questionnaire (scores 1 or 2) and those women reporting a good/excellent cosmesis result on the one item questionnaire.

16.662 Across Time

At years 1 and 2 post WBI, logistic regression modeling will be used to assess which patients, disease, and/or treatment characteristics as well as of breast lymphedema are associated with an increased likelihood of each of the following endpoint: reporting a poor to fair cosmesis, poor satisfaction with breast cosmesis, poor satisfaction with overall outcome, and poor physical well-being.

The agreement between year 1 post WBI cosmesis findings and year 2 post WBI cosmesis findings in terms of a poor to fair cosmesis, poor satisfaction with breast cosmesis, poor satisfaction with overall outcome, and poor physical well-being will be assessed using McNemar tests.

16.663 Agreement with Surgeon's Perception of Cosmetic Results at Initial Post-surgical Evaluation

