Impression of cosmesis will be dichotomized as poor to fair versus good to excellent. A 95 % confidence interval will be constructed for the proportion of cases where the patient and his surgeon agree in terms of cosmesis results.

16.664 Differences of the Extent of Disease Described on Mammography Compared with Surgical Findings

All eligible patients who have initiated surgery will be included in the analysis of this endpoint. The maximum lesion dimension and location of each lesion found on mammogram will be determined on central review. Agreement between the lesion size on mammogram and the lesion size reported on surgical pathology report will be examined using the approaches proposed by Bland and Altman. That is, a plot of the average of lesion size on mammogram and the lesion size reported on surgical pathology report versus the difference in lesion size between that found on mammogram and that found on surgery will be constructed to examine systematic biases. A 95 % z-confidence of the difference in lesion size between that found on mammogram and that found on surgery will be constructed. Percent agreement will be used to assess the extent of agreement between location of the lesion seen on mammogram and the location of the lesion reported on surgical pathology report.

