Appendix IV : Active Monitoring Patient Questionnaire Booklet

Page 1 of 7

PATIENT QUESTIONNAIRE BOOKLET – ACTIVE MONITORING

You have been given a booklet to complete for this study. The booklet contains some questions about your cosmetic result, quality of life and health status as a patient receiving treatment for cancer. Your answers will help us to better understand how the treatment you are receiving is affecting the way you feel and tolerate treatment.

1. The booklet contains three sets of questions:
 - a. 4-Point Scoring System of Breast Cosmesis (1 question)
 - b. BREAST-Q® Breast-conserving therapy (lumpectomy) Postoperative model (54 questions)
 - c. Breast Lymphedema (BLE) Symptom Survey (5 questions)
2. Directions on how to complete each set of questions are written on the top of each set.
3. Please complete the booklet during your scheduled clinic visit and return it to your nurse or your physician.

Thank you for taking the time to help us.

4-point Scoring System of Breast Cosmesis

(Winchester and Cox 1992)

Patient Questionnaire

Alliance Number: _____ Patient Initials (last, first) _____ Date: _____

You have been treated with breast conserving therapy for breast cancer. As you know, a reason for choosing this treatment is to keep a breast that looks and feels as close to normal as possible. Your opinion concerning the appearance of your breast is valuable to us. Circle the number next to the word that best describes how your breast looks now.

1	When compared to the untreated breast or the original appearance of the breast, there is minimal or no difference in the size or shape of the treated breast. The way the breast feels (its texture) is the same or slightly different. There may be thickening, scar tissue or fluid accumulation within the breast, but not enough to change the appearance.
2	There is a slight difference in the size or shape of the treated breast as compared to the opposite breast or the original appearance of the treated breast. There may be some mild reddening or darkening of the breast. The thickening or scar tissue within the breast causes only a mild change in the shape or size.
3	Obvious differences in the size and shape of the treated breast. This change involves a quarter or less of the breast. There can be moderate thickening or scar tissue of the skin and the breast, and there may be obvious color changes.

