4	Marked change in the appearance of the treated breast involving more than a quarter of the breast tissue. The skin changes may be obvious and detract from the appearance of the breast. Severe scarring and thickening of the breast, which clearly alters the appearance of the breast, may be found.

BREAST-Q®
Breast Conservation Therapy (Lumpectomy)
Postoperative Module

Alliance Number: _____ Patient Initials (last, first) _____ Date: _____

The following questions are about your breasts and your breast cancer treatment (by treatment, we mean lumpectomy with or without radiation). After reading each question, please choose the response that best describes your situation. If you are unsure how to answer a question, choose the answer that comes closest to how you feel. Enter only **one** choice per answer. Please answer **every** question. Do not leave any blank.

1. With your breast in mind, in the past 2 weeks, how satisfied or dissatisfied have you been with:

	Very Dissatisfied	Somewhat Dissatisfied	Somewhat Satisfied	Very Satisfied
a. How you look in the mirror clothed?	1	2	3	4
b. The shape of your lumpectomy breast when you are wearing a bra?	1	2	3	4
c. How normal you feel in your clothes?	1	2	3	4
d. Being able to wear clothes that are more fitted?	1	2	3	4
e. How comfortably your bras fit?	1	2	3	4
f. How equal in size your breasts are to each other?	1	2	3	4
g. How normal your lumpectomy breast looks?	1	2	3	4
h. How your lumpectomy breast sits/hangs?	1	2	3	4
i. How soft your lumpectomy breast feels to the touch?	1	2	3	4
j. How much your breasts look the same?	1	2	3	4
k. How smoothly shaped your lumpectomy breast looks?	1	2	3	4
l. The contour (outline) of your lumpectomy breast?	1	2	3	4
m. How your lumpectomy breast looks now compared to before you had any breast surgery?	1	2	3	4
n. How your breasts look in the mirror unclothed ?	1	2	3	4
o. How your lumpectomy breast looks overall ?	1	2	3	4

2. With your lumpectomy breast in mind, in the past 2 weeks, how much have you been bothered by:

	I don't have this problem	I have this problem and it bothers me...		
		Not at all	A little	A lot
a. Your lumpectomy breast being too small compared to your other breast?		1	2	3
b. Your lumpectomy breast being an irregular shape?		1	2	3
c. Your lumpectomy breast having dimpled (indented) areas?		1	2	3
d. Areas of your lumpectomy breast that look sunken in (hollow)?		1	2	3
e. How obvious your lumpectomy breast scars look?		1	2	3

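### The cosmesis analysis reverses the poor/fair score code in one sentence, tests year 1 to year 2 agreement with McNemar, lists a 1-month time with no booklet, and names subscales that need reconciling

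*Combined protocol and SAP*

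**What the plan says.** **Score code.** Section 16.661 plans a confidence interval for the proportion of patients indicating that "their cosmesis result on the one item questionnaire was poor or fair (scores: 3 or 4"). The next sentence plans a Wilcoxon rank sum test of each BREAST-Q subscale, with one group being women "reporting a poor/fair cosmesis result on the one item questionnaire (scores 1 or 2"). On the one-item form in Appendix IV, score 1 begins "When compared to the untreated breast or the original appearance of the breast, there is minimal or no difference in the size or shape", and score 4 begins "Marked change in the appearance of the treated breast involving more than a quarter of the breast tissue".

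**Year 1 versus year 2.** Section 16.662 states an aim of agreement between the two years on four dichotomised outcomes. The list ends: "poor satisfaction with overall outcome, and poor physical well-being will be assessed using McNemar tests". Elsewhere the plan handles agreement differently. For patient versus surgeon (16.663): "A 95 % confidence interval will be constructed for the proportion of cases where the patient and his surgeon agree". For lesion location (16.664): "Percent agreement will be used to assess the extent of agreement between location of the lesion seen on mammogram".

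**Times.** Section 16.66 sets assessments at the initial post-operative visit and at "1, 6, 12, and 24 months following completion of WBI".

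**Subscales.** Section 16.66 names three BREAST-Q subscales: satisfaction with breasts, satisfaction with overall outcome, and physical well-being. Section 1.242 names only the first two. Section 16.661 refers to deficits, and 16.662 to poor results, on these subscales; neither gives a cut-off.

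**The concern.** The two codes in 16.661 cannot both be right, and the form shows which is wrong. An analyst who follows the Wilcoxon sentence would label the women with the best results as poor/fair and report the difference in the wrong direction.

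McNemar uses only the two discordant counts and asks whether they are equal. It takes no account of how many women gave the same answer twice, so its p-value cannot tell a reader whether year 1 and year 2 answers agree. A non-significant result could be misread as good agreement, and a significant one as poor agreement.

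The 1-month time would have no data. One of the three subscales may not be scorable from the booklet, and without stated cut-offs the binary subscale outcomes are undefined in the plan.

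These problems fall on the analysis of patient-perceived cosmesis, a secondary endpoint named in Section 16.2.

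**Working it through.** The plan states no figure on this point that needs reproducing. The checks are comparisons of text and illustrative calculations. All counts below are assumed; none are trial data.

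**1. Score code**

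| Source | Poor/fair end |
|---|---|
| 16.661, confidence interval sentence | 3 or 4 |
| 16.661, Wilcoxon sentence | 1 or 2 |
| Appendix IV form | 1 is best, 4 is worst, so 3 or 4 |
| Section 1.241, order of the categories | runs from excellent to poor, consistent with 1 to 4 |

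Only the Wilcoxon sentence disagrees. For the effect of a full label swap, use U₁ + U₂ = n₁n₂. In simulated scores with groups of 50 and 150, U is 1740 one way and 5760 the other, and 1740 + 5760 = 7500 = 50 × 150. The two-sided p is 1.4 × 10⁻⁸ both ways; only the sign of the difference changes. The sentence gives no code for good/excellent. If only the poor/fair group followed the printed code, both groups would hold scores 1 and 2.

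**2. McNemar against agreement**

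Let a = poor/fair at both years, b = year 1 only, c = year 2 only, d = neither, and n = a + b + c + d.

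- Agreement: pₒ = (a + d)/n
- Chance agreement: pₑ = p₁p₂ + (1 − p₁)(1 − p₂), with p₁ = (a + b)/n and p₂ = (a + c)/n
- Kappa = (pₒ − pₑ)/(1 − pₑ)
- Exact McNemar: two-sided binomial test of b out of b + c against 0.5

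With 15% poor/fair at both years, pₑ = 0.15² + 0.85² = 0.745. For 20/10/10/160, kappa = (0.90 − 0.745)/0.255 = 0.61.

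For 30/2/12/156, p₁ = 0.16, p₂ = 0.21 and pₑ = 0.0336 + 0.6636 = 0.6972, so kappa = (0.93 − 0.6972)/0.3028 = 0.77. McNemar p = 2 × (1 + 14 + 91)/2¹⁴ = 212/16384 = 0.013.

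| a/b/c/d | n | McNemar p | Agreement | Kappa |
|---|---|---|---|---|
| 28/2/2/168 | 200 | 1.0 | 98% | 0.92 |
| 20/10/10/160 | 200 | 1.0 | 90% | 0.61 |
| 10/20/20/150 | 200 | 1.0 | 80% | 0.22 |
| 0/30/30/140 | 200 | 1.0 | 70% | −0.18 |
| 30/2/12/156 | 200 | 0.013 | 93% (95% CI 88.5 to 96.1) | 0.77 (0.65 to 0.88) |
| 15/1/6/78 | 100 | 0.125 | 93% (86.1 to 97.1) | 0.77 (0.61 to 0.93) |
| 0/15/15/70 | 100 | 1.0 | 70% | −0.18 |

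The n = 100 rows are there because Section 16.66 runs these analyses separately for women with and without axillary lymph node dissection (ALND). A stratum size of 100 is an assumption.

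**3. Times**

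Section 4.1 (footnote 9), Section 4.2 (footnote 4), Section 7.4 and Section 18.2 (footnote 3 to the test schedule table) all give post-WBI booklets at 6, 12, 18 and 24 months (± 1 month), then 36, 48 and 60 months (± 2 months). The earliest window is 5 to 7 months. Of the analysis times 1, 6, 12 and 24 months, only month 1 has no booklet. The post-operative booklet is timed from surgery, so it does not supply one.

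**4. Subscales**

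The BREAST-Q blocks in Appendix IV hold 15 + 11 + 14 + 14 = 54 items, matching the stated 54, so no block is missing from the text. By content they cover satisfaction with the breast, bother from the operated breast, radiation effects and physical symptoms. None appears to ask about satisfaction with overall outcome. The documents contain no key from items to scales, so this cannot be settled from them.

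**The case against.** The score code is a slip that largely corrects itself. The groups are also named in words, the preceding sentence and the form give the right code, and the proportion poor/fair is coded correctly. A result showing women with poor cosmesis as more satisfied would probably be noticed. That limits the likely harm, but the sentence is still wrong as written.

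On McNemar, the section is headed as an analysis across time, and the test is valid for a change in the proportion poor/fair. The authors may have meant change. If so, the stated aim is wrong instead of the test, and one of the two must still be altered. Kappa appears nowhere in the plan, and a proportion agreeing with its confidence interval would be enough to follow the practice of 16.663. The pooled tables of 200 do not match the planned split by ALND, and the example that is significant despite 93% agreement weakens to p = 0.125 at n = 100. This is fair. Yet agreement and kappa are identical in those two tables while p moves from 0.013 to 0.125, so the p-value is not measuring agreement. The p = 1.0 result also survives the split. The 0/30/30/140 table is extreme, but 10/20/20/150 makes the same point less starkly.

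On times, the booklet row of Table 4.2 seems to carry marks under chemotherapy and radiation. Its footnote still gives only the 6-monthly and then yearly times.

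The subscale point is weaker. Section 1.242 is background text, says the module was still being finalised, and leaves scoring for later; Section 16.661 defers to the scoring module, which could also supply cut-offs. It stands only as something to reconcile, not as a proven gap.

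**Conclusion.** The concern holds. The reversed code and the 1-month time are certain from the text. The mismatch between the stated aim of agreement and the McNemar test is also certain; its numerical size depends on assumed tables, in which p = 1.0 is compatible with agreement anywhere from 98% to 70%, and p = 0.013 with 93%. The subscale discrepancy (two against three) is certain, but whether satisfaction with overall outcome can be scored is not known without the key. The effect is confined to a secondary endpoint and the primary local recurrence analysis is untouched. The text should be corrected before the final analysis is programmed.

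**What to change.** 1. In the Wilcoxon sentence of 16.661, change the poor/fair code to scores 3 or 4, and add that good/excellent is 1 or 2.
2. In 16.662, report percent agreement and kappa with 95% confidence intervals for year 1 versus year 2, within the ALND strata the plan already uses. Keep McNemar only as a test of change, and describe it so.
3. Delete the 1-month time from 16.66 so that every listed time has a scheduled booklet.
4. Reconcile the subscale list in 16.66 with Section 1.242, Appendix IV and the BREAST-Q scoring key. Drop any subscale that cannot be scored.
5. State the cut-off for a deficit or a poor result on each retained subscale before the analysis. The planned confidence intervals, logistic models and McNemar tests need it as much as kappa does.

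Items 1 and 3, and item 2 for the one-item questionnaire, are wording changes that use data already collected. Items 4 and 5, and item 2 for the subscales, need a check against the scoring key and stated cut-offs; one planned subscale may be lost.

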7.7 Patient Follow-up After Completion of WBI

All eligible patients will enter the observation phase of this trial after completion of WBI (see test schedule, Section 4.0). At the follow-up visits, patients will complete a symptom survey and undergo a physical examination. The breast lymphedema symptom survey will assess breast heaviness, swelling, redness, and discomfort. The physical examination will assess the presence or absence of breast edema, which will combine with the symptom score to define cases of breast lymphedema. Lymphedema should be graded using CTCAE version 4.0 (see Section 10.51).

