16.65 Incidence of Breast Lymphedema (BLE)

For each time point, a 95 % binomial confidence interval for the proportion of patients diagnosed with breast lymphedema will be determined. Breast lymphedema will be defined as a patient who has a symptom survey score > 0 and presence of breast edema by physical examination.

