f. Lack of sensation (feeling) in your lumpectomy breast?		1	2	3
g. Feeling lopsided in your clothing?		1	2	3
h. The nipple and areola on your lumpectomy breast looking caved in?		1	2	3
i. The nipple and areola on your lumpectomy breast moved from its natural position?		1	2	3
j. The nipple on your lumpectomy breast pointing in an unnatural direction?		1	2	3
k. The shape of your areola looking distorted?		1	2	3

3. With your radiated breast in mind, in the past 2 weeks, how much have you been bothered by:

	I don't have this problem	I have this problem and it bothers me...		
		Not at all	A little	A lot
a. Your radiated breast skin looking different (e.g., too dark or too light)?		1	2	3
b. Your radiated areola looking different (e.g., too dark or too light)?		1	2	3
c. Marks on your breast caused by radiation (e.g., small visible blood vessels)?		1	2	3
d. Tattoo marks placed to guide the radiation treatment?		1	2	3
e. Your radiated breast skin feeling dry?		1	2	3
f. Your radiated breast skin feeling sore (sensitive) when touched (e.g., changes in water temperature when you bathe/shower)?		1	2	3
g. Your radiated breast feeling irritated by clothing that you wear?		1	2	3
h. Your radiated breast feeling uncomfortable?		1	2	3
i. Your radiated breast feeling tight?		1	2	3
j. Your radiated breast feeling heavy?		1	2	3
k. Your radiated breast feeling swollen?		1	2	3
l. Your radiated breast feeling unnaturally firm?		1	2	3
m. Hard scar tissue in your radiated breast that you can feel?		1	2	3
n. Your radiated breast skin feeling unnaturally thick (rough, tough) when you touch it?		1	2	3

4. In the past 2 weeks, how often have you experienced?

	None of the time	A little of the time	Some of the time	Most of the time	All of the time
a. Tightness in your lumpectomy breast?	1	2	3	4	5
b. Pulling in your lumpectomy breast?	1	2	3	4	5
c. Tenderness in your lumpectomy breast?	1	2	3	4	5
d. An aching feeling in your lumpectomy breast?	1	2	3	4	5
e. Sharp pains in your lumpectomy breast?	1	2	3	4	5
f. Shooting pains in your lumpectomy breast?	1	2	3	4	5
g. Neck pain?	1	2	3	4	5
h. Upper back pain?	1	2	3	4	5
i. Shoulder pain?	1	2	3	4	5
j. Arm pain?	1	2	3	4	5
k. Difficulty lifting or moving your arms?	1	2	3	4	5
l. Swelling (lymphedema) of the arm on the side that you had your lumpectomy surgery?	1	2	3	4	5
m. Difficulty sleeping because of discomfort in your lumpectomy breast?	1	2	3	4	5
n. Difficulty laying on the side of your lumpectomy breast?	1	2	3	4	5

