Breast Lymphedema (BLE) Symptom Survey
(Degnim *et al.* 2008)

Alliance Number: _____ Patient Initials (last, first) _____ Date: _____

Please answer the following questions regarding current (within the last week) symptoms in the operated breast.

1. Does your breast appear or feel swollen?

Not at all 0 1 2 3 4 5 6 7 8 9 10 A lot

2. Does your breast feel heavy?

Not at all 0 1 2 3 4 5 6 7 8 9 10 A lot

3. Is your breast redder in color?

Not at all 0 1 2 3 4 5 6 7 8 9 10 A lot

4. Do you have pain, tenderness, or discomfort in your breast?

Not at all 0 1 2 3 4 5 6 7 8 9 10 A lot

5. Do you have armpit fullness or numbness?

Not at all 0 1 2 3 4 5 6 7 8 9 10 A lot

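### Section 16.662 relates patient-reported outcomes to a breast lymphedema variable that itself requires patient-reported symptoms, so part of any association may reflect shared self-report rather than edema

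*Combined protocol and SAP*

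**What the plan says.** Section 16.662 fits logistic regressions at years 1 and 2 after whole breast irradiation (WBI). It asks which patient, disease and "treatment characteristics as well as of breast lymphedema are associated with an increased likelihood" of four outcomes: "reporting a poor to fair cosmesis, poor satisfaction with breast cosmesis, poor satisfaction with overall outcome, and poor physical well-being". All four are reported by the patient.

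Section 16.65 counts a patient as having BLE if she has a "symptom survey score > 0 and presence of breast edema by physical examination". Section 7.7 agrees: "The physical examination will assess the presence or absence of breast edema", "which will combine with the symptom score to define cases of breast lymphedema". It also gives the survey's content: "The breast lymphedema symptom survey will assess breast heaviness, swelling, redness, and discomfort". The survey form in Appendix IV adds a fifth item on armpit fullness or numbness. Each item runs from 0 to 10.

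The Appendix IV booklet holds the one-item cosmesis scale, the BREAST-Q and the BLE survey together. Section 16.66 runs its analyses separately for women with and without axillary lymph node dissection (ALND). Section 16.662 does not say which visit's BLE enters the model, and it plans no version with examination edema alone.

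**The concern.** One respondent supplies all of the outcomes and one of the two conditions that define the covariate. The survey asks "Do you have pain, tenderness, or discomfort in your breast"; BREAST-Q question 4 asks about "Tenderness in your lumpectomy breast", and about aching and pains. Every woman classed as having BLE is symptomatic by definition. Women with edema but no symptoms go into the comparison group, together with women who have neither. If symptomatic women tend to report worse outcomes for any reason, BLE will be associated with those outcomes even where edema plays no part.

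Cosmesis and BLE are both secondary goals (Sections 2.23 and 2.24), and Section 1.243 puts forward a higher BLE risk from boosting both tumor beds. A reported link between BLE and poor well-being could be read as harm from treatment-related edema when the data had shown only that complaints in one part of a booklet go with complaints in another. Section 1.243 also shows that a symptom-free definition was available: in the earlier study, BLE was diagnosed on examination without using the symptom ratings.

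**Working it through.** The plan gives no sample size, power or error rate for Section 16.662, so there is no figure to reproduce. The check isolates the mechanism.

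**Set-up.** Let e be the proportion with edema on examination and s the proportion scoring above 0 on the survey, with the two independent. Let a and b be the probabilities of a poor outcome in women scoring above 0 and in women scoring 0. Edema has no effect on the outcome. BLE means edema and a score above 0. Then:

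- probability of poor outcome with BLE = a
- probability of poor outcome without BLE = [a·s·(1−e) + b·(1−s)] / (1 − e·s)

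**Inputs.** e = 0.30, a = 0.40 and b = 0.10 are assumptions; s is varied. The total n = 200 is the evaluable cohort in Section 16.3. Because the models are split by ALND, n = 100 is shown as an assumed stratum size.

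**Worked case, s = 0.60.** Without BLE: (0.40×0.60×0.70 + 0.10×0.40) / (1 − 0.18) = 0.208/0.82 = 0.254. Odds ratio = (0.40/0.60) / (0.254/0.746) = 0.667/0.340 = 1.96.

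Rejection rates are from 20,000 simulated trials with a two-sided 5% likelihood-ratio test and BLE as the only covariate.

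| Share scoring above 0 | Poor outcome without BLE | Built-in odds ratio | Rejection, n = 200 | Rejection, n = 100 |
|---|---|---|---|---|
| 60% | 0.208/0.82 = 0.254 | 1.96 | about 41% | about 23 to 24% |
| 90% | 0.262/0.73 = 0.359 | 1.19 | about 9% | about 7% |
| 95% | 0.271/0.715 = 0.379 | 1.09 | about 6% | about 6% |
| 100% | 0.280/0.70 = 0.400 | 1.00 | about 5% | about 6% |

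With examination edema alone as the covariate, rejection is about 5% in these scenarios and the true odds ratio is 1.

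**Range.** With b = 0.10, e from 20% to 40%, s from 50% to 90% and a from 30% to 40%, the built-in odds ratio runs from 1.13 to 2.47, and rejection at n = 200 from 6% to 65%.

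**Document-based edema prevalence.** Section 1.243 gives 26/26 with and 5/38 without clinical BLE, so 31/64 = 48% had skin edema. With that e, a = 30% and b = 10%, the odds ratio is 2.12 at s = 50% and 1.19 at s = 90%.

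The effect vanishes if every woman scores above 0, or if symptoms are unrelated to the outcome (a = b).

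**The case against.** The strongest reply is that Section 16.662 asks only about association. BLE is defined as edema with symptoms, and in the worked case BLE so defined truly is associated with the outcome (40% against 25.4%). Rejecting is then correct for that question. This stands. A reader might infer that the planned odds ratio is simply biased upward and that its test rejects far too often. The documents support that only if the result is read as an effect of edema, which the plan does not claim.

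The independence of edema and symptoms is artificial. Section 1.243 reports higher symptom scores in women with examination-diagnosed BLE. If edema raised the share scoring above 0 from 50% to 90% (assumed, other inputs as before), edema alone would give 0.37 against 0.25, an odds ratio of 1.76, and the composite 2.07. Most of the association would then not be artefact. This also stands: the table isolates a mechanism and does not forecast the trial.

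The inputs are soft. Any non-zero answer on five items qualifies after surgery, WBI and boost, so s could be high and the effect small. The ALND split means that no model uses all 200 women. The documents do not give s, so the plan cannot rely on its being high either.

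It is also tempting to say that the covariate contains part of the outcome. It does not: no BREAST-Q or cosmesis item enters the BLE score. BREAST-Q question 3 does ask about heaviness and swelling, but the documents do not assign it to any of the three subscales in Section 16.66. The satisfaction items in question 1 do not ask about pain or heaviness, and the swelling item in question 4 concerns the arm. Clear overlap of content is limited to physical well-being.

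**Conclusion.** The concern holds in a limited form. Because the BLE covariate requires self-reported symptoms from the same booklet as the outcomes, a BLE association in Section 16.662 cannot by itself be attributed to edema. The point is clearest for poor physical well-being and weaker for satisfaction and one-item cosmesis. An association arises without any edema effect whenever some women score 0 and symptomatic women report worse outcomes.

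Its size is unknown. On the assumed inputs it ranges from an odds ratio of 1.96 when 60% score above 0, through 1.19 at 90%, to none at 100%. The 41% rejection rate belongs to the first case with all 200 women in one model; at an assumed stratum of 100 it is about 23 to 24%. A same-visit BLE value is a natural reading, but Section 16.662 does not state it.

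These are secondary models. The primary endpoint and the descriptive BLE proportion in Section 16.65 are unaffected. This is an inexpensive improvement in interpretation, not a flaw that threatens the trial.

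**What to change.** In Section 16.662, fit the models with breast edema on physical examination (present or absent, already assessed at follow-up under Section 7.7) as the covariate, at least as a prespecified analysis beside composite BLE. State which visit's value is used. Add that an association seen only with the composite will not be attributed to edema. Leave the Section 16.65 definition unchanged.

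The cost is a sentence or two and one extra set of secondary models, with no new data collection. There are two drawbacks. Examination edema is a different variable from the protocol's BLE construct and answers a different question. The examiner is also not stated to be blind to the patient's complaints, so the finding may not be wholly independent of self-report.
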